Appendix 3. Prohibited Concomitant Medications

All prohibited investigational compounds require discontinuation for at least 4 weeks or 5 half-lives (whichever is longer) prior the Baseline Visit.

All investigational compounds, other than study drugs (tofacitinib and MTX), are prohibited during the study.

Please refer to [Appendix 6](#) for prohibited corticosteroids.

Only systemically administered drugs listed below are prohibited; topical, ophthalmic, or intravaginal administration is allowed.

The use of folate antagonists such as trimethoprim is prohibited during the study.

Prohibited Concomitant Medications	
CYP3A4 and/or CYP2C19 Inhibitors	CYP3A4 Inducers
Protease inhibitors: indinavir (Crixivan) nelfinavir (Viracept) ritonavir (Kaletra, Norvir) Saquinavir (Invirase)	Protease inhibitors: efavirenz (Sustiva)* nevirapine (Viramune)*
Macrolide antibiotics: clarithromycin (Biaxin, Prevpac) telithromycin (Ketek)	Anticonvulsants: barbiturates* phenobarbital* phenytoin (Dilantin, Phenytek) carbamazepine (Carbatrol, Tegretol)*
Other antibiotics: chloramphenicol	Antibiotics: rifampicin/rifampin (Rifadin, Rifamate) rifabutin (Mycobutin)* Rifapentene (Priftin)*
Antifungals: fluconazole (Diflucan) ketoconazole (Nizoral) itraconazole (Sporanox) voriconazole (Vfend)	Antidepressants: St. John's Wort*
Antidepressants: fluvoxamine (Luvox) nefazodone (Serzone)	Other compounds: modafinil (Provigil) troglitazone (Rezulin)
Prohibited Concomitant DMARDs**	
Biologic DMARDs	Nonbiologic DMARDs
Rituximab, anakinra (Kineret), etanercept (Enbrel), infliximab (Remicade), abatacept (Orencia), tocilizumab (Actemra), certolizumab pegol (Cimzia®), Golimumab (Simponi TM), adalimumab (Humira),	Oral gold (auranofin), injectable gold (aurothioglucose, aurothiomalate), sulfasalazine, d-penicillamine, bucillamine, mizoribin, azathioprine, leflunomide (Arava), cyclosporine, tacrolimus, tetracyclines (unless prescribed for acne), antimalarials (chloroquine, hydroxychloroquine), baricitinib

*Discontinue for at least 30 days

** See [Section 5.8](#) for specific washout requirements.

Appendix 4. Cockcroft-Gault Formula for Estimating GFR

$$\text{Creatinine Clearance (estimated) / Conventional mL/min} = \frac{((140 - \text{Age (years)}) \times \text{Weight (kg)} \times \text{Factor}^a)}{(72 \times \text{Serum Creatinine (mg/dL)})}$$

^a Factor is equal to 0.85 in females and 1.00 in males.

Appendix 5. Approximate Equivalent Morphine Doses Of Opioid Analgesics

Common opioid analgesics

Drug	Maximum Allowed Total Daily Dose	Relative potency to oral morphine	Half-Life
Morphine	30 mg	1	1.5 – 4 hrs
Hydrocodone (Vicodin, Lortab)	30 mg	1	3.8 – 4.5 hrs
Hydromorphone (Dilaudid)	7.5 mg	4	2.5 hrs
Meperidine (Demerol, Pethidine)	300 mg	0.1	3.2 – 3.7 hrs
Methadone (Dolophine, Methadose, Physeptone)	10 mg	3.0	23 hrs
Codeine (Paveral, Tylenol #2 and #3)	200 mg	0.15	2.5 – 3.5 hrs
Oxycodone [Roxicodone; Percocet, Tylox]	15 mg	~2	3.2 hrs
Tramadol [Ultram, Zydol; Zamadol, Ultracet, Tramal]	300 mg	~0.1	4.7 – 5.1 hrs

Sites should contact project team for acceptable alternative preparations and related data.

References:

2. Twycross R. Pain relief in advanced cancer. Edinburgh: Churchill Livingstone, 1994.

Appendix 6. Rescue Therapy

Acetaminophen/ paracetamol is allowable as rescue medication if dosed no more than the locally approved recommended daily dose for no more than 10 consecutive days. If a subject is already taking stable background doses of acetaminophen/ paracetamol, s/he may increase the dose up to the locally approved recommended daily dose for up to 10 consecutive days for rescue purposes.

Acetaminophen/paracetamol is not permitted as a part of combination products such as over-the-counter “cold remedies” or in combination with opioids if the acetaminophen/paracetamol dose will exceed the locally approved recommended daily dose. Subjects who require rescue for more than 10 consecutive days should be discontinued from the trial. In addition, subjects should not be dosed with rescue acetaminophen/paracetamol or opioids within 24 hours prior to a study visit. However, baseline stable acetaminophen/paracetamol or opioids should NOT be discontinued in advance of study visits.

Low dose oral corticosteroids in doses equivalent to ≤ 10 mg prednisone per day is allowed during the study period. However, the prednisone dose increase should not exceed the initial dose during the study period.

Intra-articular corticosteroids may be given during the first 3 months of the run-in phase in no more than two joints, in a cumulative dose of no more than 80 mg methylprednisolone or its equivalent during any 6 month study period. Injections are not allowed after 3 months. Injected joints will also be considered as having their pre-injection status (tender/painful or swollen) for the remainder of the trial.

Intravenous or intramuscular corticosteroids are not allowed during this study.

Biologic response modifiers are not allowed during this study.

Subjects should not be dosed with any rescue intervention within 24 hours prior to a study visit.

The following paradigm should be used to determine appropriate opioid rescue therapy:

For subjects who are NOT on stable, background opioid therapy: any of the following single opioid agents may be given as rescue medication (with or without acetaminophen/ paracetamol) for no more than 10 consecutive days in the following total daily doses:

1. Hydrocodone, not to exceed 30 mg total daily dose.
2. Oxycodone, not to exceed 15 mg total daily dose.
3. Tramadol, not to exceed 300 mg total daily dose.

For subjects who ARE on stable, background opioid therapy:

1. They may NOT add a second opioid agent for rescue.
2. If their background medication is 1 of the 3 listed above, they may, within the above maximum total dosage limits, increase the dosage for up to 10 consecutive days for rescue purposes.
3. If their background medication is a short-acting (half-life <5 hours, [Appendix 5](#)) opioid that is not one of those listed above, they may increase the dosage for up to 10 consecutive days (up to a total daily dose which must not exceed the potency equivalent of 30 mg of orally-administered morphine ([Appendix 5](#)) for rescue purposes.
4. Sustained release opioid formulations (eg, OxyContin[®], MS Contin[®]) and opioids with half-lives greater than 5 hours (eg, methadone) may NOT be USED for rescue medication.
5. Sustained release opioid formulations (eg, OxyContin[®], MS Contin[®]) and opioids with half-lives greater than 5 hours (eg, methadone; see also [Appendix 4](#)) may NOT be INCREASED for rescue purposes.

Appendix 7. Belgium, Czech Republic, Germany, Hungary, Italy, Poland, Spain, and United Kingdom Specific Protocol Requirements

In Belgium, Czech Republic, Germany, Hungary, Italy, Poland, Spain, and the United Kingdom, the following changes are made to the protocol:

4.4.5 Contraception and Reproductive Status

In this study, male subjects who are able to father children and female subjects who are of childbearing potential will receive MTX, which has been associated with teratogenic risk in humans, and tofacitinib which has been associated with teratogenic risk in animals (further information can be found in the single safety reference document). Those who, in the opinion of the investigator, are sexually active and at risk for pregnancy with their partner(s) must agree to use with their partner(s) highly effective contraception throughout the study and continue for at least 6 months after the last dose. The investigator or his or her designee, in consultation with the subject, will select the appropriate method of contraception for the individual subject and his/her partner(s) from the list of permitted contraception methods below and instruct the subject in their consistent and correct use. The investigator or his or her designee will discuss with the subject the need to use a highly effective method of contraception consistently and correctly according to the [schedule of activities](#) and document such conversation, and the subject's affirmation, in the subject's chart. In addition, the investigator or his or her designee will instruct the subject to call immediately if a selected contraception method is discontinued or if pregnancy is known or suspected in the subject or the subject's partner.

Highly effective methods of contraception are those that, alone or in combination, result in a failure rate of less than 1% per year when used consistently and correctly (ie, perfect use).

One of the below options must be used to satisfy the requirement for highly effective contraception:

1. Established use of hormonal methods of contraception associated with inhibition of ovulation (ie, oral, inserted, injected, implanted, transdermal) with either:
 - a. male condom or female condom used WITH a spermicide (ie, foam, gel, film, cream, or suppository). For countries where spermicide is not available, this option is not appropriate;
 - b. male sterilization.
2. Correctly placed copper-containing intrauterine device (IUD) or intrauterine system combined with either:
 - a. male condom or female condom used WITH a spermicide (ie, foam, gel, film, cream, or suppository). For countries where spermicide is not available, this option is not appropriate;

- b. male sterilization.
3. Male sterilization with absence of sperm in the postvasectomy ejaculate combined with:
 - a. male condom or female condom used WITH a spermicide (ie, foam, gel, film, cream, or suppository. For countries where spermicide is not available, this option is not appropriate;
 - b. bilateral tubal ligation/bilateral salpingectomy or bilateral tubal occlusive procedure.
 4. Bilateral tubal ligation / bilateral salpingectomy or bilateral tubal occlusive procedure (provided that occlusion has been confirmed in accordance with the device's label) combined with:
 - a. IUD or intrauterine system;
 - b. male condom or female condom used WITH a spermicide (ie, foam, gel, film, cream, or suppository). For countries where spermicide is not available, this option is not appropriate;
 - c. male sterilization.

Pregnancy testing will be performed and documented at every visit unless the non-childbearing potential is confirmed and documented. The specific contraceptive methods will be documented and at every visit, their consistent and correct use will be ascertained and documented in the subject's case report form.

1. VERSION HISTORY

This Statistical Analysis Plan (SAP) for study A3921192 is based on Protocol Amendment 2 dated 04-Dec-2017.

Table 1. Summary of Major Changes in SAP Amendments

SAP Version	Change	Rationale
1	Not Applicable	Not Applicable
2	
 a. Section 7 was changed for analysis of openlabel phase b. Window of open-label Week 24 was changed as “Days 127 – Discontinuation Day /randomization (early one)” 	Based on Protocol Administrative Change Letter 05-Jul-2017
3	
 a. In Section 2.2, based on recent calculations, the number of subjects was increased from 580 to 680 for the open-label phase in order to achieve at least 232 subjects in the double-blind phase. b. The LDA assessment was changed from DAS28-4(ESR) < 3.2 and DAS28-4(CRP) < 3.2 to DAS28-4(ESR) ≤ 3.2 and DAS28-4(CRP) ≤ 3.2, in Sections 3.2, 3.3, 5.3.3, 6.2.4, 6.2.5, 6.3.3, 6.3.4 and Appendix 1.1. c. Change in tender/painful joint counts, swollen joint counts, subject assessment of arthritis pain, subject global assessment of arthritis, physician global assessment of arthritis, and CRP were added as other efficacy endpoints in Sections 3.3, 6.2.3 and 6.3.2. d. Analysis for exploratory endpoint RAPID3 was added in Section 6.4. e. Baseline Disease Characteristics of 	Based on Protocol Amendment 2 04-Dec-2017

	
prior use of tsDMARD, baseline MTX dose, baseline steroid dose, ESR, CRP, tender joint counts, swollen joint counts, pain VAS, subject global assessment, physician global assessment, DAS28-4(ESR), DAS28-4(CRP), HAQ-DI, CDAI, and SDAI were added in Section 3.5.
 
f. “Line plots of the LS means and 95% CI” was changed to “Line plots of the LS means (+/- SE)” in Section 6.
 
g. “Line plots of the percentage and 95% CI” was changed to “Line plots of the percentage (+/- SE)” in Section 6.
 
h. Observed cases were added for analyses in Section 6.
 
i. Summary of ECG was added in Section 6.7.5.
 
j. Analysis window for Week 6 was added in Appendix 1.2.
 
k. Updated analysis window for Baseline in Appendix 1.2.
	
4	
a. Added details for MMRM when the model with unstructured covariance structure doesn’t converge in Section 5.2.2.
 
b. Added details for NRI in Section 5.3.3 and Section 5.3.5.
 
c. Removed “Canada” in the region definition in Section 6.5.
 
d. Added details for subgroup MMRM model in Section 6.5.
 
e. Added details for windowing in
	To add analysis details based on BDR1 discussions

	
Appendix 1.2.
 
f. Updated the window for Randomization in Appendix 1.2
 
g. Corrected typos in the document.
	
--	--------------------------------------------------------------------------------------------------------------------------------	--

2. INTRODUCTION

The tofacitinib Immediate Release (IR) 5mg twice daily (BID) formulation has demonstrated efficacy both as a monotherapy and in combination with methotrexate (MTX) in previous trials. However, it remains unknown whether the tofacitinib efficacy will be sustained after the withdrawal of MTX among RA patients who achieve low disease activity following treatment with MTX plus tofacitinib. Results of the current study will inform the value of the continued MTX treatment among subjects who have responded to combined therapy of tofacitinib and MTX. A modified release (MR) 11mg once daily (QD) regimen has the potential to offer an additional dosing option to subjects, and based on the equivalence of key pharmacokinetic parameters, efficacy and safety are expected to be consistent with that demonstrated for tofacitinib IR 5 mg BID. Therefore, the current study will evaluate the sustained efficacy and safety of the tofacitinib MR 11 mg QD regimen among rheumatoid arthritis (RA) patients undergoing blinded withdrawal of MTX.

This SAP provides the detailed methodology for summary and statistical analyses of the data collected in study A3921192. This document may modify the plans outlined in the protocol; however, any major modifications of the primary endpoint definition or its analysis will also be reflected in a protocol amendment.

2.1. Study Objectives

2.1.1. Primary Objectives

To compare the efficacy of tofacitinib MR 11mg monotherapy to tofacitinib MR 11mg with continued MTX, as measured by the change in the Disease Activity Score utilizing 4 components including erythrocyte sedimentation rate (DAS28-4 (ESR)) from randomization (at Week 24) to the end of the double-blind MTX withdrawal phase (at Week 48).

2.1.2. Secondary Objectives

- *To compare the efficacy of tofacitinib MR 11mg monotherapy to tofacitinib MR 11mg with continued MTX in the double-blind MTX withdrawal phase (at Week 36), as measured by DAS28-4 (ESR).*
- *To compare the efficacy of tofacitinib MR 11mg monotherapy to tofacitinib MR 11mg with continued MTX in the double-blind MTX withdrawal phase (at Weeks 48 and 36), as measured by Disease Activity Score 28-4 (C reactive protein) (DAS28-4 (CRP)), Clinical Disease Activity Index (CDAI), Simplified Disease Activity Index (SDAI), Low Disease Activity (LDA), remission, ACR20, ACR 50, and ACR 70.*

- *To compare effects of tofacitinib MR 11mg monotherapy to tofacitinib MR 11mg with continued MTX on health outcome measures in the double-blind MTX withdrawal phase (at Weeks 48 and 36), as measured by Health Assessment Disability Questionnaire-Disability Index (HAQ-DI), Medical Outcomes Survey Short Form -36 (SF-36), Work Productivity and Activity Impairment (WPAI), European Quality of Life 5 dimensions questionnaire (EuroQol EQ 5D), and Functional Assessment of Chronic Illness Therapy (FACIT)-Fatigue scale.*
- *To evaluate the safety and tolerability of tofacitinib MR 11mg monotherapy versus tofacitinib MR 11mg with continued MTX.*

2.1.3. Other Objectives

- *To describe efficacy of treatment with tofacitinib 11mg with MTX in the open-label run-in phase (at Weeks 12 and 24), as measured by DAS28-4 (ESR), DAS28-4 (CRP), CDAI, SDAI, LDA, remission, ACR20, ACR 50 and ACR70.*
- *To describe effects of treatment with tofacitinib MR 11mg with MTX on health outcome measures in the open-label run-in phase (at Weeks 12 and 24), as measured by HAQ-DI, SF-36, WPAI, EuroQol EQ-5D, and FACIT-Fatigue scale.*

2.1.4. Exploratory Objectives

[figure not shown]
- *To collect exploratory biomarker/genomics samples for bio-banking.*
- *US and Canada ONLY: To explore effects of treatment with tofacitinib MR 11mg with/without MTX on health outcome measure in the open-label run-in phase (at Weeks 12 and 24) and the double-blind MTX withdrawal phase (at Weeks 48 and 36), as measured by Routine Assessment of Patient Index Data 3 (RAPID3).*

2.2. Study Design

Study A3921192 is a 12-month randomized, double-blind, placebo-controlled withdrawal study in a total of approximately 680 subjects with moderate to severe RA (defined as CDAI >10 and DAS28 (ESR) \geq 3.2) who are insufficiently responding to their stable dose of MTX treatment. In addition, the proportion of subjects who have had an insufficient response to one or more biologics prior to the enrollment should be \leq 25% (ie, \leq 145 subjects). Following enrollment, all subjects will receive open-label tofacitinib MR 11mg QD added to MTX at their previously stabilized dose for 24 weeks (run-in phase). At the end of the run-in phase (Week 24), only subjects who achieve low disease activity (LDA) as assessed by CDAI (ie, CDAI \leq 10) (approximately 232 subjects) will be randomized into the 24-week double-blind, placebo-controlled MTX withdrawal phase. Subjects who do not achieve LDA (defined by CDAI >10) at this time point will be discontinued from the study. Subjects entering the double-blind phase will be randomized in a 1:1 ratio to either continue the run-in phase treatment regimen (tofacitinib MR 11mg QD with blinded MTX) or to receive tofacitinib monotherapy (tofacitinib MR 11mg QD with blinded matching placebo for MTX). Randomization will be stratified by subject's prior exposure to a biologic DMARD (bDMARD). Randomized subjects will be followed up to the end of Week 48. The primary

efficacy endpoint is the change in DAS28-4 (ESR) from randomization (at Week 24) to the end of double-blind MTX withdrawal phase (at Week 48).

Figure 1. Study Design

3. ENDPOINTS AND BASELINE VARIABLES: DEFINITIONS AND CONVENTIONS

3.1. Primary Efficacy Endpoint(s)

Change in DAS28-4 (ESR) score from randomization (at Week 24) to the end of double-blind MTX withdrawal phase (at Week 48).

3.2. Secondary Efficacy Endpoint(s)

- Change in the DAS28-4(ESR) from Week 24 to Week 36;
- Changes in the DAS28-4 (CRP), CDAI and SDAI, respectively, from Week 24 to Week 48 and from Week 24 to Week 36;
- LDA as assessed by DAS28-4(ESR) ≤ 3.2, DAS28-4(CRP) ≤ 3.2, CDAI ≤ 10 and SDAI ≤ 11, respectively, at Weeks 48 and 36;
- Remission as assessed by ACR-EULAR Boolean remission criteria, DAS28-4 (ESR) < 2.6, DAS28-4 (CRP) < 2.6, CDAI ≤ 2.8 and SDAI ≤ 3.3, respectively, at Weeks 48 and 36;
- ACR20, ACR 50, and ACR70 responses, respectively, at Weeks 48 and 36;

- Change in the HAQ-DI, the SF-36 (8 domain scores and 2 component scores), WPAI, EuroQol EQ-5D and the FACIT-Fatigue scale score, respectively, from Week 24 to Week 48 and from Week 24 to Week 36;
- HAQ-DI response (ie, decrease of at least 0.22) at Weeks 48 and 36.
- Note:
- For subjects entering the double-blind phase, the value at randomization (Week 24) for each endpoint is the last nonmissing observation before the first dose of study drug in double-blind phase.
- The baseline (Day 1) value for each endpoint is the last nonmissing observation before the first dose of study drug in open-label run-in phase.
- ACR20, ACR 50, ACR70, and HAQ-DI responses are relative to baseline (Day 1).

3.3. Other Efficacy Endpoints

- Changes in DAS28-4 (ESR), DAS28-4 (CRP), CDAI, SDAI, HAQ-DI, SF-36 (8 domain scores and 2 component scores), WPAI, EuroQol EQ-5D score and FACIT-Fatigue scale score, respectively, from day 1 to Week 12 and from Day 1 to Week 24;
- LDA as assessed by $\text{DAS28-4(ESR)} \leq 3.2$, $\text{DAS28-4(CRP)} \leq 3.2$, $\text{CDAI} \leq 10$ and $\text{SDAI} \leq 11$, respectively, at Weeks 12 and 24;
- Remission as assessed by ACR-EULAR Boolean remission criteria, $\text{DAS28-4 (ESR)} < 2.6$, $\text{DAS28-4 (CRP)} < 2.6$, $\text{CDAI} \leq 2.8$ and $\text{SDAI} \leq 3.3$, respectively, at Weeks 12 and 24;
- ACR20, ACR 50, and ACR70 responses, respectively, at Weeks 12 and 24;
- HAQ-DI response (ie, decrease of at least 0.22) at Weeks 12 and 24.
- Change in tender/painful joint counts, swollen joint counts, subject assessment of arthritis pain, subject global assessment of arthritis, physician global assessment of arthritis, and CRP, respectively, from Day 1 to Week 12 and from Day 1 to Week 24, from Week 24 to Week 48 and from Week 24 to Week 36.

3.4. Exploratory Endpoints

- *US and Canada ONLY: RAPID3 summary scores at Weeks 12, 24, 36 and 48.*

3.5. Baseline Variables

Demographic and baseline characteristics include:

- Age (in years);

- Sex;
- Race;
- Region;
- Height (in cms);
- Weight (in kg);
- Body Mass Index;
- Duration of disease (in years);
- Rheumatoid Factor (positive/negative);
- Anti-cyclic citrullinated peptide (Anti-CCP) antibody (positive/negative);
- Prior use of bDMARD (yes/no);
- Prior use of TNFi (yes/no);
- Prior use of MTX (yes/no);
- Prior use of csDMARD (yes/no);
- Prior use of tsDMARD (yes/no);
- Prior use of corticosteroid (yes/no);
- Baseline MTX dose;
- Baseline Steroid Dose;
- Disease activity (moderate or severe based on DAS28-4(ESR) at baseline);
- DAS28-4(ESR);
- DAS28-4(CRP);
- ESR;
- CRP;
- Tender Joint Counts;
- Swollen joint Counts;
- Subject global assessment;
- Physician global assessment;
- Pain VAS;
- HAQ-DI;
- CDAI;
- SDAI.

Note: Prior use of bDMARD will be used in the mixed-effect model of repeated measures (MMRM) model as a covariate. It will be based on the CRF data.

3.6. Safety Endpoints

3.6.1. Adverse Events

- *All adverse events (AEs), including serious adverse events (SAEs).*
- Adjudicated safety events

An AE is considered treatment emergent relative to a given treatment if:

- the event occurs for the first time during the effective duration of treatment and was not seen prior to the start of treatment, or
- the event was seen prior to the start of treatment but increased in severity during treatment.

The effective duration of treatment is determined by the lag time. Any event occurring within 28 days, whether this occurs during a break in treatment or at the end of treatment, is attributed to the corresponding treatment period.

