2.1.2. Secondary Objectives

- To compare the efficacy of tofacitinib MR 11mg monotherapy to tofacitinib MR 11mg with continued MTX in the double-blind MTX withdrawal phase (at Week 36), as measured by DAS28-4 (ESR).
- To compare the efficacy of tofacitinib MR 11mg monotherapy to tofacitinib MR 11mg with continued MTX in the double-blind MTX withdrawal phase (at Weeks 48 and 36), as measured by Disease Activity Score 28-4 (C reactive protein) (DAS28-4 (CRP)), Clinical Disease Activity Index (CDAI), Simplified Disease Activity Index (SDAI), Low Disease Activity (LDA), remission, ACR20, ACR 50, and ACR 70.

- To compare effects of tofacitinib MR 11mg monotherapy to tofacitinib MR 11mg with continued MTX on health outcome measures in the double-blind MTX withdrawal phase (at Weeks 48 and 36), as measured by Health Assessment Disability Questionnaire-Disability Index (HAQ DI), Medical Outcomes Survey Short Form -36 (SF-36), Work Productivity and Activity Impairment (WPAI), European Quality of Life 5 dimensions questionnaire (EuroQol EQ 5D), and Functional Assessment of Chronic Illness Therapy (FACIT)-Fatigue scale.
- To evaluate the safety and tolerability of tofacitinib MR 11mg monotherapy versus tofacitinib MR 11mg with continued MTX.

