6.7. Safety Summaries and Analyses

6.7.1. Adverse Events

Adverse events will be summarized according to Pfizer data standards for each phase.

- TEAEs;
- Serious AEs;
- Serious infections;
- Adjudicated events.

AEs will not be double counted across phases. Counting of AEs will be based on start date of AE. If the start date of an AE is in the open-label phase, the end date of the AE in the double-blind phase and severity of AE remained the same or became lower in both phases, then the AE will be counted in open-label phase, not in the double-blind phase. However, if the same AE started in the open-label phase, and get worse in severity in the double-blind phase, then the AE will be counted in both phases.

In all these analyses attention will be restricted to assessments that occurred no more than 28 calendar days after the last dose of study drug.

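### SAP 3.6.1 and 6.7.1 give different answers for double-blind TEAEs when an event resolves in the run-in and recurs after randomisation, and the 28-day lag is not reconciled with the start-date rule

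*SAP*

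**What the plan says.** SAP 3.6.1 defines emergence by treatment. "An AE is considered treatment emergent relative to a given treatment if" one of two conditions is met. The first is that "the event occurs for the first time during the effective duration of treatment and was not seen prior to the start of treatment". The second is that "the event was seen prior to the start of treatment but increased in severity during treatment". The section does not say whether, for a randomised subject, treatment starts on Day 1 or at the first double-blind dose. It does not mention events that resolve and come back.

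The same section adds a lag: "Any event occurring within 28 days, whether this occurs during a break in treatment or at the end of treatment" is assigned to the matching treatment period. It does not say what happens to the lag when a subject passes directly from the run-in to the double-blind phase.

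SAP 6.7.1 sets the rule for counting by phase: "AEs will not be double counted across phases. Counting of AEs will be based on start date of AE". It works through one situation only, a single AE that begins in the open-label phase and carries on into the double-blind phase. If it does not worsen, it counts in the open-label phase alone. If it worsens, it counts in both.

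Protocol 2.1.2 includes the objective "To evaluate the safety and tolerability of tofacitinib MR 11mg monotherapy versus tofacitinib MR 11mg with continued MTX". Protocol 9.5 splits all safety displays by phase, so the double-blind TEAE table is where the two regimens are compared for non-serious events.

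**The concern.** Every randomised subject has already spent 24 weeks on tofacitinib plus MTX. Suppose a subject has nausea at Week 10, recovers, and has nausea again at Week 30 at the same severity. The second episode begins after randomisation, on the randomised regimen. Under 3.6.1 it is not a first occurrence and it has not worsened, so it is not treatment emergent. Under 6.7.1 its start date places it in the double-blind phase.

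Two programmers could therefore build different double-blind TEAE tables from the same data and each cite the SAP. What is at stake is whether onsets after randomisation stay in the randomised tolerability comparison, and whether that is settled before the arms are known. The lag adds to the problem, because MTX is withdrawn in full, without tapering, at randomisation (Protocol 5.5). The first 28 days are when the regimens first differ.

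**Working it through.** **Step 1. The two rules side by side.** The middle column takes the randomised regimen as the treatment of reference and reads 3.6.1 literally.

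| Case | SAP 3.6.1 | SAP 6.7.1 | Agree? |
|---|---|---|---|
| First-ever onset at Week 30 | Emergent | Double-blind | Yes |
| Starts in run-in, ongoing at first double-blind dose, not worse | Not emergent | Open-label only | Yes |
| Starts in run-in, ongoing, then worsens | Emergent | Both phases | Yes |
| Week 10, resolved, again at Week 30, same severity | Not emergent | Double-blind (new start date) | **No** |
| As above, second episode more severe | Emergent | Double-blind | Yes |
| First-ever onset 14 days after first double-blind dose | Emergent, but the lag could assign it to the run-in | Double-blind | **Not if the lag is read literally** |

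Taking Day 1 as the start of treatment does not clearly resolve the fourth row. The run-in is then no longer a pre-treatment period, but the Week 30 episode is still not the first occurrence.

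**Step 2. The lag.** The double-blind phase lasts 24 weeks = 168 days, and 28/168 = 16.7%.

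**Step 3. Figures in the plan.** The documents give no AE rate, recurrence rate or expected AE difference. The only related figure is the randomised sample size (Protocol 9.1), used here for arm size alone. Per arm, n = 2 × (1.960 + 1.282)² × 1.4² / 0.6² = 114.4, so 115 per arm or 230 in total, against the stated 232. At 116 per arm the power is 90.4%, against the stated 90%. The figure reproduces, but it does not bear on this point.

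**Step 4. Effect on the arm contrast.** Notation:
- q: share of randomised subjects who had the event in the run-in and recovered.
- a: recurrence risk in the double-blind phase among those subjects.
- b: risk of a new event in the others.
- C: continued MTX. M: monotherapy.

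Recurrences are taken to be no more severe than before.

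- Start-date counting: RD = q(a_C − a_M) + (1 − q)(b_C − b_M)
- Literal 3.6.1: RD = (1 − q)(b_C − b_M)
- Removed by the literal rule: q(a_C − a_M)

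Assumed for illustration: b_C = 10%, b_M = 6%. Each start-date cell gives the RD in points, with the risk ratio in brackets.

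| Assumed recurrence, C vs M | q = 5% | q = 10% | q = 20% |
|---|---|---|---|
| 40% vs 20%, start date | 4.8 (1.72) | 5.6 (1.76) | 7.2 (1.82) |
| 30% vs 30%, start date | 3.8 (1.53) | 3.6 (1.43) | 3.2 (1.30) |
| 20% vs 40%, start date | 2.8 (1.36) | 1.6 (1.17) | −0.8 (0.94) |
| Any of these, literal 3.6.1 | 3.8 (1.67) | 3.6 (1.67) | 3.2 (1.67) |

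For example, q = 10% in the first row gives C = 0.10 × 0.40 + 0.90 × 0.10 = 13.0% and M = 0.10 × 0.20 + 0.90 × 0.06 = 7.4%, so RD = 5.6. The literal rule gives 9.0% − 5.4% = 3.6. At 116 per arm, that is 15.1 and 8.6 subjects by start date against 10.4 and 6.3 under the literal rule.

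**Step 5. A second model.** A share s of subjects is susceptible, with risk r per phase on MTX and r/2 off it. True rates are s·r and s·r/2. The literal rule multiplies both by (1 − r).

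| s, r (assumed) | RD by start date | RD literal | Risk ratio, both |
|---|---|---|---|
| 1, 0.1 | 5.0 | 4.5 | 2.0 |
| 0.33, 0.3 | 4.95 | 3.47 | 2.0 |
| 0.2, 0.5 | 5.0 | 2.5 | 2.0 |

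Here the absolute difference shrinks, but the ratio does not move because both arms are scaled equally.

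**The case against.** The best defence is that 6.7.1 governs the tables. It says "Counting of AEs will be based on start date of AE", and the only case it removes from the double-blind phase is an AE that began earlier, continued and did not worsen. A recurrence has its own start date and would be counted. The TEAE tables also follow sponsor data standards that are not in the documents and may already define emergence by phase. Both points are fair. They show that the likely intention is sensible, but not that the SAP states it. 6.7.1 lists TEAEs among its displays and so depends on the definition in 3.6.1, whose wording excludes the recurrence.

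On the lag, the sentence concerns a break in treatment or its end. Randomised subjects receive double-blind supplies at Visit 4 and stay on tofacitinib, so no break is planned there. That makes the literal reading less natural. It does not rule it out, because the run-in regimen does end at that visit for the monotherapy arm.

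On scope, 6.7.1 lists serious AEs, serious infections and adjudicated events separately from TEAEs. SAP 3.6.2 gives laboratory values with change from both baseline and randomisation at Weeks 36 and 48. This stands: the problem is shown only for the TEAE display.

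The treatment of AEs ongoing at randomisation is explicit in 6.7.1 and defensible, since it avoids charging earlier onsets to a randomised arm. It is not part of this point.

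**Conclusion.** The conflict is real and follows from the text alone. For a same-severity recurrence after a resolved run-in episode, 3.6.1 read literally excludes what 6.7.1 includes, and neither section addresses the case. How the 28-day lag ends at the phase change is also left open.

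A reader might go further and infer that the SAP designates the run-in as the pre-treatment period, and that the safety comparison is therefore biased toward no difference. The documents do not support that. 3.6.1 never names the run-in as preceding treatment; that is one reading of an undefined term. Both arms share the same run-in and the same rule. The absolute difference shrinks if recurrence is more common on MTX, is unchanged if recurrence is equal, and widens or changes sign if it is more common on monotherapy. With equal recurrence the risk ratio moves away from 1, and in the susceptible-share model it stays at 2.0. All these rates are assumptions, and the high per-phase risks sit uneasily with an entry requirement of at least 4 months on MTX.

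The supportable conclusion is that the literal rule drops post-randomisation onsets from the TEAE comparison. This can shrink the risk difference, but the direction and size are unknown. The primary efficacy analysis is untouched. The point should be settled before unblinding, so that the choice between two written rules is not made with the arms known.

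**What to change.** Add three statements to SAP 3.6.1 for double-blind displays:

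1. An AE whose onset is on or after the first double-blind dose is treatment emergent for that phase, even if the same event occurred and resolved in the run-in.
2. The worsening condition applies only to AEs still ongoing at the first double-blind dose.
3. For randomised subjects, the open-label 28-day lag stops at the first double-blind dose.

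This aligns 3.6.1 with the start-date rule and leaves the ongoing-AE rule in 6.7.1 as it is. The cost is a few lines of SAP text. The existing counting rules already rely on start date, end date and severity, so no new data are needed. The small downside is that double-blind TEAE counts may rise slightly in both arms. A table by arm of AEs ongoing at randomisation and whether they resolved would be informative in a withdrawal design, but it is optional.
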